5.3.6.2.4 Binary Responses

For secondary response endpoints the following parameters will be defined:

Positive Symptomatic Response

Positive Symptomatic Response is defined as relief of neuroglycopenic symptoms (ANS) within 30 minutes from a decision to dose.

Positive Treatment Response

Positive Treatment Response is defined as exhibiting either a positive plasma glucose response (PGR) or a positive symptomatic response.

The following secondary response endpoints will be assessed.

1. Rate of failing to achieve a Positive Plasma Glucose Response 1 (PGR1).
2. Rate of failing to achieve a Positive Plasma Glucose Response 2 (PGR2).
3. Rate of failing to achieve a Positive Symptomatic Response.
4. Rate of failing to achieve a Positive Treatment Response.

For these secondary endpoints, analysis will be the same that for primary endpoint (PGR) described above in [section 5.3.6.1](#). Actual time will be used for calculations.

5.3.6.3 Safety Variables

All Safety and Tolerability assessments will be performed using the Safety Population.

5.3.6.3.1.1 Adverse Events (AE)

All verbatim AE terms will be coded using the Medical Dictionary for Regulatory Activities (MedDRA, latest version) and summarized by System Organ Class (SOC) and Preferred Term (PT). AE collection will begin from the time of informed consent.

Time periods for Adverse Events

Adverse Events will be attributed to analysis phases and periods by time of onset.

Treatment Emergent Adverse Events (TEAEs) will be defined as AEs not present prior to the start of study procedures, or AEs present before study medication that worsened after starting of study procedures at Day 1 prior to first dose administration. If a partially missing date or time of onset allows the possibility that an AE may be a TEAE it will be assumed that it is a TEAE.

TEAEs will be analyzed by treatment and in overall. TEAEs will be attributed to study treatment which was administered before the AE onset within the respective Treatment Period 1 or 2.

Each TEAE will be attributed to Treatment Period 1 or 2. If TEAE started at the time of Day 1 Pre-dosing procedures of second dose, it will not be attributed to Treatment Period 1, but will be counted in the Overall TEAE summary.

AEs will be summarized by treatment, period and in overall by the number and percentage of subjects who experienced at least one AE of the following categories in each treatment group: any AE, any AE from CRC admission to the time of induction, any AE from time of induction to treatment, any TEAE, any drug related TEAE, any severe or life-threatening TEAE, any serious TEAEs, any drug-related SAE, any SAE leading to death, any TEAE leading to study discontinuation, and any SAE leading to study discontinuation.

AEs will be tabulated by SOC and PT in each category.

TEAEs will be summarized by highest relationship to study drug (Not Related, Related) and maximum severity (Mild, Moderate, Severe). If severity of AE is missing, then the AE will be analyzed as 'Severe'. If relationship to study drug for the AE is unknown, then the TEAEs will be classified as Related, and non-TEAEs will be classified as Not Related.

AEs will be analyzed for safety according to the study treatment received in corresponding treatment period and overall. All AEs will be summarized by actual treatment sequence, treatment period (Treatment Period 1 / Treatment Period 2) and overall. Subjects will be counted only once in the Overall analysis.

Listings of all AEs, SAEs, and TEAEs leading to study drug discontinuation will be provided with treatment group, site, subject, then in chronological order displaying treatment period, verbatim term, MedDRA SOC and PT, start and end dates, seriousness flag and category, severity, relationship to study drug, action taken, contributing factors, and outcome.

5.3.6.3.2 Laboratory safety assessments

Laboratory values (chemistry and hematology) will be flagged if outside the normal range and a listing of clinically significant abnormal values will be presented.

Normality ranges and evaluation should be consistent across the study.

Laboratory measurements will be summarized with descriptive statistics for actual value and change from baseline.

Baseline will be defined as last assessment before the first dose administration. Summaries will be presented by actual treatment received.

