10.2.1.1. Day -1

Clinic Arrival

1. Plasma glucose (via glucose meter) will be assessed. If the result is > 350.0 mg/dL (19.44 mmol/L), no further procedures should be performed, and the visit should be rescheduled after a minimum 24-hour wait.
2. The subject will be questioned regarding any changes in concomitant medications will be documented in the eCRF, and it will be confirmed that the subject is not receiving a medication that is exclusionary.
3. Women of childbearing potential will receive a urine pregnancy test, which must be negative before further participation is allowed.

If it has been more than 30 days since Visit 1 (i.e., the visit is occurring outside of the allowed time window), venous blood will be collected for a repeat of baseline hematology and serum chemistry assessments. However, the visit may continue based on qualification at the Screening visit.

Note: At check-in for Visit 3, venous blood will be collected for a repeat of hematology and serum chemistry assessments as baseline for the first dose of study glucagon.

4. Full vital signs will be assessed after a 5-minute seated rest. It will be confirmed that the subject continues to meet eligibility requirements for SBP and DBP. Other assessments of vital signs will be made during the visit as specified in the footnotes to [Table 5](#).

Evening Meal in Clinic

1. A standardized healthy meal will be provided to the subject (see Section [7.1](#)) with a goal of completion by 9 pm.
2. The subject should follow their normal prescribed regimen for insulin per PI discretion, including meal-time correction, until midnight.

10.2.1.2. Day 1

Overnight Monitoring (starting at approximately midnight)

1. Subjects will be instructed to fast, taking nothing but water and oral glucose tablets if necessary, starting at approximately midnight and will be monitored for compliance by the CRC staff.
2. An IV catheter will be placed in one arm, maintenance fluids will be started, and the subject's insulin pump will be discontinued, if applicable. If use of an overnight IV is not possible due to site staffing considerations, use of the subject's own insulin infusion pump or SC insulin will be used overnight.

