13.5. Safety Analysis

All safety analyses will be performed using the safety population, namely those subjects receiving at least one dose of the study drug.

The following variables will be compared between the treatment groups for safety purposes:

- AEs and SAEs
- Laboratory safety variables (Screening to Final Visit)
- Physical examination (Screening to Final Visit)
- Vital signs
- Body weight (Screening to Final Visit)
- ECG (Screening to Final Visit)
- Local tolerability, including:
 - Subjective injection site discomfort as reported by subjects using a 100-mm visual analog scale (VAS) and ordinal pain scales ([Appendix 2](#)).
 - Erythema and or edema formation at site of injection assessed using the Draize scale ([Appendix 3](#)).

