5.2 Reference Dates, Analysis Periods, Analysis Visits, and Baseline

There will be two treatment periods defined and analyzed, which starts from study drug administration and the associated clinical phases associated, related with the pre-dose study procedure:

SCREENING/BASELINE, RUN-IN (1 and 2), TREATMENT PERIOD (1 and 2).

- SCREENING/BASELINE: analysis phase starts with Informed Consent, includes Day -1 check-in before first drug administration.

Baseline will be defined as the last assessment within this phase and used as the reference point for safety assessments across the study to each of the visits (laboratory data, ECG, physical examination, weight, temperature and respiratory rate).

- PRE-TREATMENT PERIOD 1: analysis phase will be assigned only if subject failed to achieve hypoglycemic steady state and study drug was not administered at the first treatment visit. It will start from first overnight monitoring to last check-in before first drug administration inclusively.

Baseline 1 will be defined as last assessment at Day -1 of Treatment 1 and will be used as the reference point for safety assessments within Treatment Period 1 (HR and BP).

- RUN-IN 1: analysis phase starts from Day 1 of Treatment 1 study procedures prior to first drug administration and continues until the first drug administration or study discontinuation, whichever comes first.
- TREATMENT PERIOD 1: analysis phase/period starts from first drug administration to check-in of the next treatment visit or study discontinuation, whichever comes first.
- PRE-TREATMENT PERIOD 2: analysis phase will be assigned only if subject failed to achieve hypoglycemic steady state and the subject's second study drug was not injected at the first treatment visit after the end of Treatment Period 1. The period will start from first overnight monitoring after the end of Treatment Period 1 to last check-in before second drug administration inclusively.

Baseline 2 will be defined as last assessment at Day -1 before Treatment 2 and used as reference point for safety assessments within Treatment Period 2 (HR and BP).

- RUN-IN 2: analysis phase starts from Day 1 of Treatment 2 study procedures prior to second drug administration and continues until the second drug administration or study discontinuation, whichever comes first.
- TREATMENT PERIOD 2: analysis period/phase starts from second dose administration to the end of study.

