5.3.6.3.5 Vital signs

Vital signs (temperature, respiration, heart rate and BP after >5 mins seated rest) will be summarized for actual values and change from baseline with descriptive statistics by scheduled timepoints.

Temperature and respiration will be analysed by treatment sequence and by actual treatment received with baseline defined as last assessment before first drug administration.

Change from baseline will be assessed within period only. Summaries will be presented by treatment sequence and by actual treatment received.

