APPENDIX 1: LIST OF TABLES, LISTINGS AND FIGURES

Tables	
Number	Title
14.1.1.1	Summary of Patient Disposition (All Enrolled Patients)
14.1.1.2	Summary of Patient Disposition by Treatment (Intent-to-Treat Population)
14.1.1.3	Summary of Analysis Populations (All Randomized Patients)
14.1.2	Summary of Demographic and Baseline Characteristics (Intent-to-Treat Population)
14.1.3.1.1	Summary of Vital Signs – Blood Pressure and Heart Rate by Treatment (Safety Population)
14.1.3.1.2	Summary of Vital Signs – Blood Pressure and Heart Rate by Treatment Sequence (Safety Population)
14.1.3.2.1	Summary of Vital Signs – Weight, Respiratory Rate and Temperature by Treatment (Safety Population)
14.1.3.2.2	Summary of Vital Signs – Weight, Respiratory Rate and Temperature by Treatment Sequence (Safety Population)
14.1.4	Summary of Treatment Exposure (Intent-to-Treat Population)
14.1.5	Summary of Medical History (All Randomized Patients)
14.2.1.1.1.1	Summary of Patients Having Positive Plasma Glucose Response by Treatment (Intent-to-Treat Population)
14.2.1.1.1.2	Summary of Patients Having Positive Plasma Glucose Response by Treatment (Modified Intent-to-Treat Population)
14.2.1.1.1.3	Summary of Patients Having Positive Plasma Glucose Response by Treatment (Per-Protocol Population)
14.2.1.1.2.1	Summary of Patients Having Positive Plasma Glucose Response 1 by Treatment (Intent-to-Treat Population)
14.2.1.1.2.2	Summary of Patients Having Positive Plasma Glucose Response 1 by Treatment (Modified Intent-to-Treat Population)
14.2.1.1.2.3	Summary of Patients Having Positive Plasma Glucose Response 1 by Treatment (Per-Protocol Population)
14.2.1.1.3.1	Summary of Patients Having Positive Plasma Glucose Response 2 by Treatment (Intent-to-Treat Population)
14.2.1.1.3.2	Summary of Patients Having Positive Plasma Glucose Response 2 by Treatment (Modified Intent-to-Treat Population)
14.2.1.1.3.3	Summary of Patients Having Positive Plasma Glucose Response 2 by Treatment (Per-Protocol Population)
14.2.1.1.4.1	Summary of Patients Having Positive Symptomatic Response by Treatment (Intent-to-Treat Population)
14.2.1.1.4.2	Summary of Patients Having Positive Symptomatic Response by Treatment (Modified Intent-to-Treat Population)
14.2.1.1.4.3	Summary of Patients Having Positive Symptomatic Response by Treatment (Per-Protocol Population)
14.2.1.1.5.1	Summary of Patients Having Positive Treatment Response by Treatment (Intent-to-Treat Population)

Tables	
Number	Title

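### For subjects given both drugs, the Follow-up laboratory change is measured from before the first dose but reported under the second drug, although a Visit 3 sample could serve as the period 2 baseline

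*SAP*

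**What the plan says.** **Laboratory rule.** SAP 5.3.6.3.2 states: "Baseline will be defined as last assessment before the first dose administration. Summaries will be presented by actual treatment received". SAP 5.2 makes the pre-first-dose value the "reference point for safety assessments across the study to each of the visits", and names laboratory data, ECG, physical examination, weight, temperature and respiratory rate. A second baseline, taken at check-in before the second dose, is also defined, but it is "used as reference point for safety assessments within Treatment Period 2 (HR and BP") only.

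**Which drug a value belongs to.** SAP 5.1.5 takes actual treatment by period for the Safety population. SAP 5.2 runs Treatment Period 2 from the second dose to the end of the study and attributes assessments in a period to that period's drug. SAP Table 3 puts the Visit 3 check-in in Treatment Period 1 and Visit 4 (Follow-up) in Treatment Period 2, with an optional Follow-up row in Treatment Period 1.

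**What is collected.** Protocol Table 5 and Section 10.2.2 require hematology and chemistry at Visit 3, and Section 10.2.3 requires them at Follow-up. Protocol 10.2.1.1 describes the Visit 3 sample as "a repeat of hematology and serum chemistry assessments as baseline for the first dose of study glucagon". Table 5 schedules weight only at Visits 1 and 4.

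**Comparison intended.** Protocol 13.5 introduces its list with "The following variables will be compared between the treatment groups for safety purposes" and defines laboratory values, physical examination, weight and ECG as Screening to Final Visit.

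**Vital signs.** SAP 5.3.6.3.5 gives temperature and respiration a baseline before the first drug administration, then says "Change from baseline will be assessed within period only".

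**The concern.** The secondary objective is the safety and tolerability of G-Pen versus GlucaGen Hypokit, and secondary endpoint 10 compares the treatments on changes in laboratory variables, among others. In a crossover, a change shown under one drug should cover an interval containing only that drug's dose. The Follow-up laboratory change of a two-dose subject does not: it starts before dose 1 and ends after dose 2.

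Among two-dose subjects the second drug identifies the sequence. The Follow-up column headed G-Pen is therefore the GlucaGen-then-G-Pen sequence, and the column headed GlucaGen is the other sequence. The drug label claims more than the numbers can show. If part of the first drug's effect persists, each column contains some of the other drug's effect and the two move toward each other. No by-sequence laboratory table is listed in SAP Appendix 1 that would let a reader see this.

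**Working it through.** No sample size, power or alpha figure in the plan bears on this point, so there is nothing to reproduce. The check traces the rules and then shows what they do algebraically.

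**Tracing a two-dose subject**

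| Sample | Baseline used | Booked to | Doses in the interval |
|---|---|---|---|
| Visit 3 check-in | before dose 1 | first drug (SAP 5.2, Table 3) | first only |
| Follow-up | before dose 1 (SAP 5.3.6.3.2, 5.2) | second drug (SAP 5.1.5, 5.2, Table 3) | both |

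The first row is sound. The second is the problem. No single sentence of the SAP assigns Follow-up laboratory values to the second drug; this follows from the period definition and the attribution rule together.

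**Effect on the by-drug contrast**

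Let G-Pen shift a laboratory value by g and GlucaGen by h, and let a fraction r of the first-dose shift remain at both Visit 3 check-in and Follow-up. All three are assumptions.

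- G-Pen then GlucaGen: Follow-up change = r·g + h, booked to GlucaGen.
- GlucaGen then G-Pen: Follow-up change = g + r·h, booked to G-Pen.
- Planned contrast, G-Pen minus GlucaGen = (g + r·h) - (r·g + h) = (1 - r)(g - h).

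Subtracting the Visit 3 value (r·g or r·h) leaves h and g, so the contrast is g - h. With g = 10 and h = 0 units:

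| r | G-Pen, planned | GlucaGen, planned | Difference, planned | Difference, Visit 3 baseline |
|---|---|---|---|---|
| 0 | 10 | 0 | 10 | 10 |
| 0.25 | 10 | 2.5 | 7.5 | 10 |
| 0.5 | 10 | 5 | 5 | 10 |
| 1 | 10 | 10 | 0 | 10 |

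**When the residual is not stable**

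Let the remaining fraction be r3 at Visit 3 and rF at Follow-up. The planned contrast is (1 - rF)(g - h). With the Visit 3 baseline it is (1 + r3 - rF)(g - h). If r3 = 0.5 and rF = 0.25, the planned difference is 10 × 0.75 = 7.5 and the Visit 3-based difference is 10 × 1.25 = 12.5: equal errors in opposite directions. With a decaying residual, the Visit 3 baseline has the smaller error only when r3 is less than 2·rF.

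**How many subjects**

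The plan randomizes 122 and aims for 111 evaluable in both periods, so 111/122 = 91% would have the two-dose interval and 122 - 111 = 11 might not.

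**Timing**

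The Visit 3 value follows dose 1 by 7 to 28 days; the Follow-up value comes 2 to 7 days after dose 2. One drug column therefore mixes two post-dose intervals under either baseline.

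**The case against.** **Persistence may be negligible.** Each drug is one 1 mg dose, Protocol 6.4 describes glucagon as having a very short half-life, and the washout is 7 to 28 days. If nothing persists, r = 0 and the planned table is unbiased. This stands: the size of the bias is unknown and may be zero. A reader might infer that a real difference will be hidden, but that is the r = 1 end of an assumed range and the documents do not support it as a prediction. Still, the summaries should not rest on an unstated assumption about persistence when the separating sample is already drawn.

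**Part of the remedy is already there.** A reader might infer that the Visit 3 sample goes unused, or that every Follow-up change is misattributed. Neither holds. SAP Table 3 already books the Visit 3 value to the first drug, and a subject who stops after one dose can have Follow-up in Treatment Period 1, correctly under the only drug received.

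**ECG and physical examination.** From the list in Protocol 13.5 a reader might infer that these are compared by drug. The SAP, which takes precedence, plans only listings for both (5.3.6.3.3, 5.3.6.3.6, Listings 16.2.11 and 16.2.12). What remains is a Protocol wording mismatch.

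**Weight, temperature and respiration.** SAP 5.3.6.3.4 names no by-drug split for weight; that rests on the title of Table 14.1.3.2.1, a by-sequence version is also planned, and SAP Section 8 allows titles and structures to change. The within-period sentence in 5.3.6.3.5 can be read as governing heart rate and blood pressure alone. These are points of wording.

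**The alternative baseline has its own assumption.** It isolates the second drug only if the first drug's residual is stable between Visit 3 and Follow-up. This is correct and must be stated with the tables.

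**Consequence.** The laboratory summaries carry no test or margin. Clinically significant values are listed, and clinically significant changes become adverse events that are attributed by onset. This limits the weight of the point.

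**Conclusion.** The point holds for subjects who receive both doses. Their Follow-up laboratory change covers both drugs and is reported under the second, while Baseline 2, which would confine the change to the second dose, is restricted to heart rate and blood pressure. Under the assumed model the by-drug contrast at Follow-up is multiplied by 1 - r, from no distortion at r = 0 to none of the contrast remaining at r = 1. The full correction with a Visit 3 baseline assumes the same residual at Visit 3 and Follow-up.

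Three smaller defects go with it. Protocol 10.2.1.1 calls a sample drawn after dose 1 a baseline for dose 1. SAP 5.3.6.3.5 gives temperature and respiration two incompatible instructions for period 2 if its within-period sentence is meant to cover them. Weight has no measurement between the doses, so a drug-specific weight change cannot be formed for two-dose subjects.

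This is minor: the affected laboratory summaries are descriptive and the primary analysis is untouched.

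**What to change.** 1. In SAP 5.2 and 5.3.6.3.2, extend Baseline 2 to chemistry and hematology. Use the Visit 3 check-in sample as the baseline for the change to Follow-up under the period 2 drug, and keep it as the post-dose value for the period 1 drug.
2. Show the cumulative change from the pre-first-dose baseline to Follow-up overall or by sequence only, and add that shell to Appendix 1.
3. Footnote the laboratory tables: period 1 values are taken 7 to 28 days after dosing and Follow-up values 2 to 7 days after dosing, and the period 2 change isolates the second drug only if any first-drug residual is stable between Visit 3 and Follow-up.
4. Reword Protocol 10.2.1.1 so that the Visit 3 sample is the post-dose assessment for the first dose and the baseline for the second.
5. In SAP 5.3.6.3.5, state one period 2 baseline for temperature and respiration. Protocol Table 5 schedules both at all visits, so a Visit 3 value exists.
6. Remove weight from Table 14.1.3.2.1, keep that table for temperature and respiration, and present weight change overall or by sequence.
7. Align the list in Protocol 13.5 with the SAP: listings for ECG and physical examination, no by-drug weight comparison, and the laboratory comparison as in items 1 and 2.

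The cost is wording and table shells. No new sample or visit is needed.

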5.3.6.3.3 Physical Examination

Subjects with any findings in the physical examination evaluation at Screening will be listed.

5.3.6.3.4 Body Weight

Body weight and change from baseline to end of study will be summarized with descriptive statistics. Baseline is defined as last assessment before first drug administration.

5.3.6.3.5 Vital signs

Vital signs (temperature, respiration, heart rate and BP after >5 mins seated rest) will be summarized for actual values and change from baseline with descriptive statistics by scheduled timepoints.

Temperature and respiration will be analysed by treatment sequence and by actual treatment received with baseline defined as last assessment before first drug administration.

Change from baseline will be assessed within period only. Summaries will be presented by treatment sequence and by actual treatment received.

5.3.6.3.6 Electrocardiogram (ECG)

ECG assessment and Investigator's evaluations will be displayed in a data listing.

5.3.6.3.7 Local Tolerability

Summaries for tolerability will be presented by treatment and tabulated by scheduled timepoints. Worst post-baseline cases or scores will be determined for each subject and analyzed, which will include all scheduled and unscheduled assessments, if any.

5.3.6.3.7.1 Injection Site Discomfort

The incidence of any injection site discomfort reported by the subject will be analysed descriptively with counts and percentages for all scheduled time points.

- None
- Any injection site discomfort (including 'Other');
- Pain;
- Itching;
- Tingling, twitching or numbness;
- Irritation.

The following descriptive statistics will be provided for all timing variables for subjects reporting at least one injection site discomfort:

- Counts and percentages of time of onset from study drug injection (0-<1 min, 1-2 mins, 3-5 mins, 6-9 mins, >=10 mins);
- Total duration of discomfort will be analysed with descriptive statistics for continuous variables.

5.3.6.3.7.2 Draize Scale (Erythema and Edema)

[figure not shown]
The incidence of erythema and edema will be analysed descriptively with counts and percentages by scheduled timepoints, worst post-baseline score, and by the categories indicated below:

Erythema Formation		Edema Formation	
Description	Score	Description	Score
No erythema	0	No edema	0
Erythema	1-4	Edema	1-4
Very slight erythema: Barely perceptible	1	Very slight edema: Barely perceptible	1
Well defined erythema	2	Well defined edema	2
Moderate erythema	3	Moderate edema: raised approx. 1mm	3
Severe erythema: Beet redness to slight eschar formation	4	Severe edema: raised more than 1mm and beyond exposure area	4

Subject will be counted only once per actual treatment and timepoint and once for worst post-baseline score or erythema/edema occurrence.

5.3.6.3.7.3 VAS

VAS is reported using a 100-mm scale.

VAS scores will be summarized by all timepoints and worst post-baseline score.

Mean VAS scores will be compared between the treatments. Comparison between the treatments will be performed using a mixed model with treatment, period and treatment*period as fixed factors and subject as a random factor. This analysis will be performed on the Safety population.

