13.5.6. Local Tolerability

The incidence of any injection site discomfort (score > 0 on the ordinal rating scale) will be analyzed descriptively. The incidences of erythema and edema will be analyzed in a similar manner. Descriptive statistics (only) will be provided for time of onset and duration (of discomfort) and discomfort description (i.e., pain, irritation, itching, etc.). Mean VAS scores will be compared between the treatments.

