APPENDIX 2. INJECTION SITE DISCOMFORT ASSESSMENT

Visual Analog Scale (VAS) for Injection Site Discomfort

Investigative Site Instructions: The subject should complete the 100-mm Visual Analog Scale (VAS) for Injection Site Discomfort at 30±5 and 90±5 minutes after injection of study drug, and again at 180±5 minutes after injection of study drug. The 180-minute evaluation after injection of study drug is still required even if glucose monitoring ends at an earlier timepoint. The subject will complete the VAS by drawing a single vertical line through the scale corresponding to the perceived intensity (severity) of discomfort according to the instructions below. The goal is for the subject to report the amount of discomfort, if any, remaining at each time point, as opposed to reporting the transient pain associated with needle insertion.

[figure not shown]
Note: If a subject is unable to physically complete the questionnaire, the subject will indicate the point on the VAS corresponding to their level of discomfort, and study staff will enter a vertical line at that point. Documentation will be provided on each completed questionnaire as to who completed the form.

Please verify the length of the VAS line to be 100-mm before providing it to the subject.

Subject Instructions: Ignoring any pain from insertion of the needle, please draw a single vertical line through the scale below that corresponds to the intensity (severity) of any discomfort you are feeling **right now** at the study drug injection site.

Discomfort could include stinging, burning, tingling, throbbing or pain. The further to the right you make your vertical mark, indicates the more intense discomfort you are feeling.

You should normally draw a straight line across the scale to indicate your current level of discomfort. However, if you are currently feeling no discomfort, you should circle the vertical line on the left end of scale (above the word “no”). If you are currently feeling the worst discomfort possible, you should circle the vertical line on the right end of the scale.

Injection Site Discomfort Description and Duration Questionnaire

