Study Personnel Instructions: Question 1a should be completed by the subject at 30±5 minutes after injection of study drug. Any subject reporting discomfort other than “none,” should complete Question 1b at the same time. All subjects should also answer Question 1c at the end of the visit (180 ±5 mins post-injection). The goal is for the subject to report the qualitative nature and duration of discomfort, if any, associated with injection of study drug, ignoring any transient pain associated with needle insertion.

Note: If a subject is unable to physically complete the questionnaire, the subject will provide verbal responses, which will be recorded on the questionnaire by study staff. Documentation will be provided on each completed questionnaire as to who completed the form.

Subject Instructions: Please answer question 1a and, if applicable to you, questions 1b and 1c. In answering these questions, you should ignore any pain from insertion of the needle.

1a. How would you describe any discomfort you felt from the study drug? (Check **all** that apply):

- None (**Please ignore question 1b.**)
- Pain (e.g., throbbing, soreness, muscle ache)
- Itching
- Tingling, twitching or numbness
- Irritation (e.g., burning, stinging)

Other or additional comments: _____

1b. About how long did the discomfort last after the injection? (Check one):

- Less than 1 minute
- 1-2 minutes
- 3-5 minutes
- 6-9 minutes
- at least 10 minutes (**Please complete question 1c before leaving the clinic.**)

1c. In total, how long did the discomfort last after the injection? (Please enter a number below):

_____ Minutes

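### The SAP tabulates injection-site discomfort by time of onset, but its five time bands are those of a question about duration, and no instrument shown collects onset

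*SAP*

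**What the plan says.** SAP 5.3.6.3.7.1 (Injection Site Discomfort) lists two timing summaries for subjects who report at least one kind of discomfort. The first is categorical: "Counts and percentages of time of onset from study drug injection", in the bands "0-<1 min, 1-2 mins, 3-5 mins, 6-9 mins, >=10 mins". The second is total duration, summarized as a continuous variable.

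Protocol 13.5.6 names the same two quantities: "Descriptive statistics (only) will be provided for time of onset and duration (of discomfort".

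The data come from the questionnaire in Protocol Appendix 2. Question 1a asks what kind of discomfort was felt. Question 1b asks "About how long did the discomfort last after the injection" and offers five time bands. Question 1c asks "In total, how long did the discomfort last after the injection" and takes a number of minutes. The staff instructions give the purpose: "The goal is for the subject to report the qualitative nature and duration of discomfort". The tolerability endpoint in Protocol 5.3.2 and SAP 3.3.2 likewise names discomfort and its duration. Onset is not part of it.

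**The concern.** A table headed time of onset needs a measurement of when discomfort started, and none is visible. The bands the SAP attaches to that heading are those of a duration question. If the programmer fills the rows from 1b, a subject whose discomfort lasted 10 minutes or more is reported as having discomfort that began at 10 minutes or later, which is a different clinical statement. If the programmer instead looks for a true onset variable, the rows are empty.

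The questionnaire outputs carry more weight here than usual. Under Protocol 12.2, injection site reactions count as adverse events only if a skin reaction or pain needs medical intervention, so most discomfort will be visible only in the VAS and questionnaire summaries. Protocol 6.4 also reports that in one earlier study, XSGP-201 in healthy subjects, injection site pain was significantly more frequent with the sponsor's formulation than with a different glucagon comparator. How long discomfort lasts on each product is therefore something a reader will want to see correctly labelled.

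**Working it through.** No sample size, power or alpha figure is involved. The check is a comparison of texts.

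**Step 1: match the bands.**

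| SAP 5.3.6.3.7.1, labelled onset | Appendix 2, question 1b, duration |
|---|---|
| 0 to <1 min | under 1 minute |
| 1-2 min | 1-2 minutes |
| 3-5 min | 3-5 minutes |
| 6-9 min | 6-9 minutes |
| >=10 min | 10 minutes or more |

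All 5 of 5 bands agree. The set of subjects agrees too: the SAP limits the summary to those reporting some discomfort, and Appendix 2 sends to 1b those who answered anything other than none.

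**Step 2: look for any item that records onset.**

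- Question 1a: nature of the discomfort. No time.
- Question 1b: how long it lasted, in bands.
- Question 1c: how long it lasted in total, in minutes.
- VAS: "The goal is for the subject to report the amount of discomfort, if any, remaining at each time point", at 30, 90 and 180 minutes, each within 5 minutes. The earliest reading is at 30 - 5 = 25 minutes. It cannot place onset in any of the first four bands, which all end before 10 minutes.

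Items that collect onset: 0 of 4.

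**Step 3: check whether duration is reported elsewhere.** It is. The next SAP bullet summarizes total duration as a continuous variable, which corresponds to question 1c. Listing 16.2.9.2 also presents the questionnaire under a title that names description and duration.

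**Step 4: check whether 1c will be complete.** The protocol gives three different rules.

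- The Appendix 2 staff instruction: "All subjects should also answer Question 1c at the end of the visit".
- The Appendix 2 subject form: 1b and 1c are to be answered if applicable, and only the last 1b option (10 minutes or more) carries a direction to 1c.
- Protocol 10.2.1.2: the questionnaire is updated before discharge if discomfort is still present at 30 minutes.

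If subjects follow the form, 1c would be filled mainly by those with discomfort of 10 minutes or more. For shorter episodes, 1b would then be the only record of duration, and those are the answers the SAP appears to place under onset.

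**The case against.** The SAP never names question 1b as its source, and neither the eCRF nor the table shells are in the documents. Protocol 13.5.6 lists onset and duration as two items, so the authors may have intended two variables. This stands as a limit on certainty: the link to 1b is an inference from identical bands and the absence of an onset item. It does not remove the problem. If 1b is not the source, the plan promises a variable that no instrument shown collects.

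It can also be said that little depends on the table. That stands as well. Protocol 13.5.6 makes these summaries descriptive only, the label is the same for both treatments, and the counts for each treatment would still be there to compare, although read as the wrong quantity.

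A reader might infer more than the documents support:

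- *That the label reverses the result.* Onset and duration are different quantities, not opposites. This is mislabelling.
- *That duration is lost.* It is planned as a continuous summary. The open question is only whether 1c is complete for short episodes.
- *That several earlier studies showed more injection-site pain than another glucagon.* Protocol 6.4 reports that comparison for XSGP-201 only. Study XSGO-201 reports more erythema and edema, XSMP-202 compared with oral glucose, and the two adult Phase 3 summaries describe safety findings as generally similar.

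**Conclusion.** The mismatch is real and minor. Five of five bands labelled as onset are the answer options of a duration question, and no instrument shown collects onset. Followed as written, the SAP would appear to give either categorical duration under the wrong name or rows with no data. Potentially affected are the banded answers of every subject who completes 1b, on both treatments. The primary non-inferiority analysis, every planned test and the continuous duration summary as planned are untouched by the label.

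The conclusion rests on two assumptions: that the eCRF follows Appendix 2 and has no separate onset field, and that the banded summary is meant to draw on 1b. If the first fails, the onset rows could be populated, but the categorical duration from 1b would still have no planned summary in SAP 5.3.6.3.7.1. The possible gap in 1c is a secondary point; its size depends on which instruction sites follow, which the documents do not settle.

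**What to change.** - In SAP 5.3.6.3.7.1, relabel the banded summary as duration of discomfort (question 1b). Keep total duration from 1c as the continuous summary.
- Remove time of onset from SAP 5.3.6.3.7.1 and Protocol 13.5.6, unless the sponsor can point to an eCRF item that records it; if so, cite that item in the SAP. The SAP takes precedence (Protocol 13.1, SAP 2), so its edit governs the analysis. The protocol edit keeps the two documents consistent.
- Reconcile the Appendix 2 staff instruction, the subject form and Protocol 10.2.1.2 on who completes 1c, and state in the SAP how many subjects with discomfort contribute to the continuous summary.

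Cost: SAP and protocol wording and a row label in the tolerability table. The planned title of Table 14.3.5.2 does not mention onset and can stay. Relabelling needs no new data or analysis.
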